### **11.4.3 Exploratory Analyses**

1. Using the ATP-5 analysis population, mean changes in PCT levels at Visit 3 relative to baseline will be computed for placebo versus azithromycin, in addition to an estimated difference in mean PCT changes and associated 95% confidence intervals. Significance of a difference in mean PCT changes between treatment groups will be tested by a Wilcoxon test. Details of the analysis will be described in the SAP.
2. Using the ATP-5 analysis population, logistic regression will be used to test whether changes in PCT levels at Visit 3 relative to baseline are associated with clinical improvement at Visit 3, after accounting for treatment assignment.
3. The Day 11 DOORs (an ordinal outcome defined in Section 3.2.3) will be compared between the placebo and azithromycin arms. The sum of the probability that a randomly selected subject will have a better DOOR if assigned to the placebo arm plus one-half the probability of equal DOORs will be estimated. The null hypothesis to be tested is that the probability is equal to 0.50 (lack of superiority of azithromycin therapy). The analysis will be carried out using the ITT analysis population, with missing DOOR values (treated as continuous) imputed using multiple imputation, utilizing linear regression models. The analysis will be repeated using the ATP-11 population. At minimum, the imputation model will utilize available information collected at baseline and any completed study visits. Further details of the imputation model will be described in the SAP. The Mann-Whitney U statistic will be combined across the imputed datasets to give the test statistic and Rubin's Rules used to define distribution of the test statistic under the null hypothesis. A point estimate of the estimand will be computed by dividing combined test statistic by the number of pairwise comparisons and a 95% confidence interval of the estimand will be computed by inverting the described test of the null hypothesis.
4. Using the ATP-11 analysis population, forest plots of 95% confidence intervals for the difference in proportions of subjects with each solicited event (a component of DOOR) collected through Visit 4, for each severity threshold (mild or greater, moderate or greater, or severe) will be generated. Tests for differences in proportions between treatment arms will be given by Fisher's exact tests.
5. Using the ATP-11 analysis population, a forest plot of 95% confidence intervals for the difference in proportions of subjects with one or more visits to an ED, one or more visits to an outpatient clinic, or one or more visits to an urgent care center or one or more hospitalizations for persistent or worsening LRTI at any time after randomization (a component of clinical improvement and DOOR) will be generated. Tests for differences in proportions between treatment arms will be given by Fisher's exact tests.
6. Using the ATP-11 analysis population, for each qualifying symptom (cough, sputum production, chest pain, or difficulty breathing) and for fever, improvement in the symptom or fever at Visit 4 compared to baseline in subjects with the symptom or fever will be

analyzed. A forest plot of 95% confidence intervals for the difference in proportions of subjects with improvement in the symptom or fever will be generated. Tests for differences in proportions between treatment arms will be given by Fisher's exact tests.

7. Using the ATP-11 analysis population, for each qualifying symptom (cough, sputum production, chest pain, or difficulty breathing), deterioration in the symptom at Visit 4 compared to baseline will be analyzed in subjects having the symptom at baseline. A forest plot of 95% confidence intervals for the difference in proportions of subjects with deterioration in the symptom will be generated. Tests for differences in proportions between treatment arms will be given by Fisher's exact tests.
8. Using the ATP11 analysis population, the proportion of subjects with fever in the 24 hours preceding or at Visit 4 (fever is defined as  $\geq 37.8$  °C or 100.0 °F, measured anywhere on the body), unless related to a new process that is unrelated to the prior diagnosis of LRTI will be analyzed. A forest plot of 95% confidence intervals for the difference in proportions of subjects with fever in the 24 hours preceding or at Visit 4 will be generated. Tests for differences in proportions between treatment arms will be given by Fisher's exact tests.

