### Exploratory:

1. To compare PCT levels at Day 1 and Day 5 among treatment failures in the placebo and azithromycin groups
2. To compare the efficacy of azithromycin versus placebo in subjects with suspected LRTI and PCT levels of  $\leq 0.25$  ng/mL at Day 11 using a superiority approach, employing the "Response Adjusted for Days of Antibiotic Risk (RADAR)" methodology.
3. To compare groups receiving azithromycin versus placebo in regard to solicited events by Day 11.
4. To compare groups receiving azithromycin versus placebo in regard to hospitalization or visits to an ED, outpatient clinic, or urgent care center for worsening or persistent LRTI after randomization by Day 11.
5. To compare groups receiving azithromycin versus placebo in regard to improvement in vital sign abnormalities or symptoms present at enrollment, on Day 11.
6. To compare groups receiving azithromycin versus placebo in regard to new symptoms on Day 11, or deterioration in symptoms relative to the enrollment visit on Day 11.

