### 3.2.3 Exploratory Outcome Measures

1. Mean change in PCT levels from Day 1 and Day 5 among subjects in the placebo and azithromycin groups and among subjects with clinical improvement and clinical failures in each treatment group
2. Response Adjusted for Days of Antibiotic Risk (RADAR) analysis at Day 11 (as described for Day 5 in Section 3.2.2 except temperature will be the only vital sign assessed at Day 11)
3. Proportion of subjects reporting solicited adverse events from Day 1 to Day 11 in each treatment group
4. Proportion of subjects reporting one or more hospitalization or visits to an ED, outpatient clinic, or urgent care center for worsening or persistent LRTI from Day 1 through Day 11 in each treatment group
5. The proportion of subjects exhibiting improvement in at least two presenting signs or symptoms at Day 11 in each treatment group
6. The proportion of subjects exhibiting at least one new symptom on Day 11 in each treatment group. The proportion of subjects with a deterioration of one or more symptom relative to enrollment at Day 11 in each treatment group.

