### 9.5.2 Individual Halting Rules (Termination of Study Product Administration)

Study product administration may be discontinued if any of the following criteria are met:

- Any clinical adverse event (AE), intercurrent illness, or other medical condition occurs that, in the opinion of the investigator, continued receipt of study product would not be in the best interest of the subject;
- New onset of illness or condition that meets exclusion criteria, at the investigator's discretion
- Inadequate clinical response that requires off-study antimicrobial therapy.
  - Subjects who require off-study antimicrobial therapy will be defined as having an inadequate clinical response.

Subjects may stop study drug treatment at any time of their own volition or at the advice of their treating provider or the study investigators. Subjects who stop study product for any reason will be regarded as having withdrawn from treatment but not as having withdrawn from the study (i.e, subjects will be asked to continue to participate in follow-up visits). All subjects with an inadequate clinical response will be referred to a non-study healthcare provider for evaluation and possible treatment outside of the clinical study. If requested, unblinding can occur if clinically indicated as determined by the treating clinician and the study's site investigator.

At the time of withdrawal, subjects will undergo an early termination visit if they are not willing to participate in the remaining follow-up visits.

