### 11.2 Sample Size Considerations:

The study will be powered to the primary endpoint of clinical improvement with 560 participants included in the according-to-protocol analysis population at Day 5. To achieve this sample size, approximately 674 enrolled subjects will need to be randomized (1:1) to placebo or azithromycin treatment to have 80% power to rule out a 12.5% increase in the clinical improvement rate with antibiotic therapy compared to placebo assuming a clinical improvement rate of 57.6% in each group using a two-sided 95% confidence interval with continuity correction, in a per-protocol analysis (i.e., allowing for 16.9% loss in each treatment group to follow up/rescue medication).

The primary analysis will include an intention-to-treat (ITT) estimation of the difference in proportions of subjects with clinical improvement at Day 5 in the antibiotic and placebo groups with a two-sided 95% confidence interval.

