## **11.4 Final Analysis Plan**

The intention-to-treat (ITT) analysis population will consist of all randomized subjects. According-to-protocol (ATP) analysis populations will consist of subjects with no major protocol deviations regarding inclusion/exclusion criteria that consumed 5 doses of study product by Visit 3. The first dose of study drug should be taken within 24 hours of randomization. Subjects who miss a scheduled dose but resume the recommended dosing schedule within 24 hours remain eligible for ATP. However, in order for a subject to be eligible for the ATP-5 analysis, Visit 3 should be performed on or after the last day of study drug consumption while remaining within the 5+3 window. The ATP-5 analysis population will have the further restriction that the subjects must have completed an in-person Visit 3 within the protocol-defined time window. The ATP-11 analysis population will consist of the ATP analysis population with the further restriction that the subjects must have completed Visit 4 within the protocol-defined time window. The ATP-28

analysis population will consist of the ATP analysis population with the further restriction that the subjects must have completed Visit 5 within the protocol-defined time window.

Unless otherwise stated, all hypothesis tests and confidence intervals will be two-sided with  $\alpha=0.05$ . Statistical tests and confidence intervals will not correct for multiplicity.

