8.3. Exploratory Efficacy Analyses

8.3.1. Analysis of PCT Levels at D5V Using ATP-5 Analysis Population

Using the ATP-5 analysis population, mean changes in PCT levels at D5V relative to baseline will be computed for placebo versus azithromycin, in addition to an estimated difference in mean PCT changes from

baseline and associated 95% CI based using bootstrap with 10000 samples. The bootstrap CI estimates will use the 2.5th and 97.5th percentiles of samples obtained by repeatedly re-sampling the empirical distribution of PCT changes from baseline with replacement for each treatment group. A similar approach will be used to estimate 95% CI for difference in mean PCT changes from baseline for placebo relative to azithromycin based. Significance of a difference in mean PCT changes for placebo compared to azithromycin will be tested by a Wilcoxon test and results will be reported in [Table 62](#) for all subjects and separately for subjects with clinical failure and clinical improvement. As the limit of quantitation is 0.05, PCT values reported as <0.05 will be imputed as half the limit of quantitation (i.e; 0.025) for this analysis. Individual subject PCT levels are provided in [Listing 12](#).

8.3.2. Association of Changes in PCT Levels at D5V and Clinical Improvement Using ATP-5 Analysis Population

The relationship between changes in PCT levels at D5V relative to baseline and clinical improvement at D5V will be assessed using logistic regression adjusting for treatment assignment and centered study day of D5V as covariates. Note that PCT values reported as <0.05 will be imputed as half the limit of quantitation (i.e; 0.025) for this analysis. Results will be reported in [Table 63](#).

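### The exploratory PCT analysis is meant to describe treatment failures but is run only in ATP-5, which drops failures who stopped study product before the fifth dose

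*Protocol*

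**What the plan says.** Exploratory objective 1 (Protocol 3.1, repeated in SAP 3.1.3) is: "To compare PCT levels at Day 1 and Day 5 among treatment failures in the placebo and azithromycin groups". The matching outcome measure (Protocol 3.2.3, SAP 3.2.3) is mean change in PCT by arm and also "among subjects with clinical improvement and clinical failures in each treatment group".

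Protocol 11.4.3 item 1 sets the population: "Using the ATP-5 analysis population, mean changes in PCT levels at Visit 3 relative to baseline will be computed for placebo versus azithromycin". Item 2 uses the same set for the association with outcome: "Using the ATP-5 analysis population, logistic regression will be used to test whether changes in PCT levels at Visit 3 relative to baseline". SAP 8.3.1 adds results "separately for subjects with clinical failure and clinical improvement", still within ATP-5. SAP 8.3.2 fits the logistic model in ATP-5 as well.

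The ATP sets, from which ATP-5 is drawn, are limited to subjects who "consumed 5 doses of study product by Visit 3" (Protocol 11.4). SAP 6.3 lists the same exclusion, together with a late first dose and dosing not resumed within 24 hours of a missed dose. Use of a non-study antibiotic is not itself on that list.

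Protocol 9.5.2 names an inadequate response needing off-study antimicrobials as a ground for stopping study product, and adds: "Subjects who require off-study antimicrobial therapy will be defined as having an inadequate clinical response". The same section, and Protocol 5.4.3, keep such subjects in the study. Protocol 7.3.2 schedules a PCT sample at Visit 3. Protocol 11.2 describes the shortfall between randomised and per-protocol numbers as "allowing for 16.9% loss in each treatment group to follow up/rescue medication".

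**The concern.** The objective names a group defined by outcome (failures), while the analysis set is defined partly by treatment completion. The two are connected, because failing is one of the protocol's own reasons for not completing treatment. A subject who fails, is switched to another antibiotic and stops study product before the fifth dose can be left out of the analysis of failures because of the failure.

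What the tables would then describe is PCT in failures who still completed the course. The logistic model in SAP 8.3.2 inherits the same selection. If early stopping for failure differs between placebo and azithromycin, the omitted share differs by arm too, and the between-arm comparison within failures is affected as well as the level.

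These are the only planned analyses of change in PCT by outcome. Clinical improvement and DOOR each have an ITT version; PCT change does not. A reader interested in whether subjects with a low Day 1 PCT who later failed showed any change would look here.

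**Working it through.** **Inputs.** Randomised: 674, allocated 1:1 (Protocol 11.2). Planned ATP-5: 560, or 280 per arm (Protocol 5 and 11.2, SAP 6.6). Loss: 16.9% per arm. Assumed clinical improvement: 57.6% in each arm (Protocol 11.2, SAP 5).

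**The plan's own figure.** 560 / (1 − 0.169) = 673.9, rounded up to 674. This reproduces the stated number randomised, at 674 / 2 = 337 per arm.

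**Planned outside ATP-5.** 337 − 280 = 57 per arm (114 in all).

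**Failures expected inside ATP-5.** 280 × (1 − 0.576) = 118.7, about 119 per arm.

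**Share of sampled failures omitted.** Let s be the fraction of the 57 who are failures, stopped before the fifth dose, and have a Visit 3 PCT. The omitted share is 57s / (118.7 + 57s). The documents do not split the 16.9% by reason, so every s is an assumption:

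| s (assumed) | omitted failures per arm | omitted share |
|---|---|---|
| 10% | 5.7 | 5.7 / 124.4 = 4.6% |
| 25% | 14.25 | 14.25 / 133.0 = 10.7% |
| 50% | 28.5 | 28.5 / 147.2 = 19.4% |
| 100% (ceiling) | 57 | 57 / 175.7 = 32.4% |

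Nothing in the documents sets a floor, so the share could be below 4.6%.

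**Unequal arms, illustration only.** Take 25% of the 114, or 28.5 subjects, split 70:30 between placebo and azithromycin. Placebo omits 19.95 / (118.7 + 19.95) = 14.4% and azithromycin 8.55 / (118.7 + 8.55) = 6.7%. The split is assumed, not documented.

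**Who is and is not dropped, by rule:**
- Failure on symptoms, vital signs or fever, five doses taken: kept.
- Failure with rescue antibiotic, five doses taken by Visit 3 (Day 5 to Day 8): kept.
- Failure who stopped before the fifth dose, for rescue or any other reason: dropped, even with a Visit 3 PCT.
- Failure with no Visit 3 sample: contributes nothing under any choice of set.

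**Is the gap covered elsewhere?** Listings 5, 12, 16 and 19 show exclusion reasons, PCT values, outcome and medically attended visits by subject. An excluded failure with a sample could be found there, but no planned table or model includes that subject.

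**The case against.** The strongest case for leaving the plan alone has several parts.

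First, rescue is not an ATP exclusion. Only subjects who also fell short on dosing are lost, so most failures are likely to be kept. That stands, and it limits the point to stopped failures.

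Second, the 16.9% covers much more than rescue. Protocol 5 and 11.3.2 describe withdrawal, a missed Visit 3 and other ATP criteria; SAP 6.3 adds visits out of window or not in person and insufficient data. That also stands, and is why only a range can be given.

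Third, the inadequate response in Protocol 9.5.2 is not the same as failure in SAP 8.3.1, which is absence of Day 5 clinical improvement. For antibiotics, that endpoint needs a medically attended visit with an antibiotic given for LRTI. The groups overlap without being identical. The Visit 3 sample is scheduled rather than guaranteed, and Protocol 7.3.5 allows a withdrawing subject to finish with a phone call.

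Fourth, ATP-5 is the stated set for the Day 5 component analyses and avoids mixing in incomplete dosing. Comparing arms within failures is not a randomised comparison in any set. True, but this does not make ATP-5 the population that the objective names.

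A reader might go further and infer that the dropped failures are those most likely to show a rising PCT, so that the analysis leans toward no signal. The documents do not support that. They give no PCT trajectories by rescue status, and an antibiotic started before Visit 3 could itself change the Day 5 value. For the same reason no bias in ng/mL can be calculated.

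**Conclusion.** The mismatch is real and minor. The stated population is treatment failures; the analysed population is failures who met the ATP-5 rules, including five doses by Visit 3. Selection is on a post-randomisation event linked to failure, and no planned analysis covers those left out.

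About 5% to 19% of sampled failures would be omitted if 10% to 50% of the 57 per arm outside ATP-5 are stopped failures with a sample, with an arithmetic ceiling of 32%. This rests on the planned numbers, on the 57.6% improvement rate applying within ATP-5, and on an assumed fraction that the documents do not give. The direction and size of any bias in mean PCT change are unknown. It should not be read as a claim that all rescued failures are excluded, or that a PCT rise is being hidden.

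The analysis is exploratory. The non-inferiority conclusion rests on the ITT analysis of clinical improvement and is untouched.

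**What to change.** In Protocol 11.4.3 items 1 and 2 and SAP 8.3.1 and 8.3.2, make the main set for Tables 62 and 63 all randomised subjects with Visit 1 and Visit 3 PCT values and a determined Day 5 clinical improvement status, grouped by randomised arm whatever the number of doses taken. Keep the ATP-5 version beside it as a sensitivity analysis. Add a short table of ATP-5 exclusions by arm, failure status and use of rescue antibiotics, so the assumed fraction above is replaced by a count. SAP Table 64 already uses an available-data set, so the approach is not new to the plan.

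Separately, reconcile the wording on stopping study product: Protocol 9.5.2 is permissive, while 5.4.3 and 6.3 are worded as mandatory. The difference affects how many failures fall short of five doses.

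The cost is SAP wording, a further run of two exploratory tables and one small table; no new data are needed. The downside is that the broader set includes PCT values measured after rescue antibiotics, which is why the ATP-5 version should stay alongside, and the comparison of arms within failures remains non-randomised.

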6.6. Interim Analyses and Data Monitoring

There will be no interim analysis of efficacy or futility. An interim analysis was performed to assess the assumptions used for sample size calculations including rate of adequate clinical improvement, rate of evaluable subjects, and the frequency of enrolled subjects with PCT ≤ 0.25 ng/mL.

Assumptions underlying the original target sample size of 420 subjects were assessed by a planned, interim, blinded analysis after 213 subjects completed or terminated from the study. The original assumptions were that the overall rate of clinical improvement at Visit 3 would be 80% and that there would be no more than 15% unevaluable subjects (i.e. withdraw, fail to complete D5V or didn't meet other inclusion criteria for the according-to-protocol population at Day 5). In this interim analysis, the required sample size needed for 80% power to rule out a 12.5% increase in the clinical improvement rate with antibiotic therapy compared to placebo was computed using the observed overall rate of clinical improvement across both treatment groups and the observed proportion of subjects eligible for an according-to-protocol analysis at D5V. The findings of the interim analysis concluded that 674 subjects needed to be randomized to achieve an ATP-5 sample size of 560 (280 per arm) to achieve 80% power using clinical improvement rate of 57.6% in each group allowing for 16.9% loss in each treatment group. The protocol was updated to reflect the updated sample size.

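### The exploratory PCT analysis reports a Wilcoxon p-value as the significance of a difference in means, which is not what that test tests

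*Protocol*

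**What the plan says.** Protocol 11.4.3 item 1 computes mean PCT changes at Visit 3 by arm, "in addition to an estimated difference in mean PCT changes and associated 95% confidence intervals", and then names the test: "Significance of a difference in mean PCT changes between treatment groups will be tested by a Wilcoxon test". It leaves details to the SAP.

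SAP 8.3.1 keeps the pairing. The interval is a percentile bootstrap ("associated 95% CI based using bootstrap with 10000 samples"), and the test sentence reads "Significance of a difference in mean PCT changes for placebo compared to azithromycin will be tested by a Wilcoxon test". It also states that "PCT values reported as <0.05 will be imputed as half the limit of quantitation", i.e. 0.025.

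Table 62 puts the two results in one row: footnote b is the bootstrap CI for the difference in mean changes and footnote c is the Wilcoxon p-value. The row appears for clinical improvement, clinical failure and all subjects. Protocol 11.4 sets the level: "all hypothesis tests and confidence intervals will be two-sided with" α = 0.05. The documents say only Wilcoxon; since independent arms are compared, it must be the rank-sum (Mann-Whitney) test.

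**The concern.** A rank-sum test and a difference in means address the same null only if the two distributions have the same shape and differ by a shift. That is hard to believe here. Baseline is bounded above by the entry limit, many low values are tied by the substitution rule, and a large change can only be a rise. A few large rises move the mean a good deal and the ranks very little. A small movement in most subjects does the opposite.

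At stake is what Table 62 can be made to say. A reader who takes the p-value as described could conclude that mean PCT change does not differ beside a CI that excludes 0, or that it differs when the means are practically equal. SAP 8.2.9 to 8.2.13 warn that CI and p-value may be inconsistent for the pairs of Fisher's test with a Miettinen-Nurminen interval. SAP 8.3.1 carries no such warning, although here the two results concern different nulls.

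**Working it through.** **Figure to reproduce.** None. The documents give no power, effect size or PCT distribution for this comparison.

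**Inputs from the documents.** ATP-5 size 280 per arm (SAP 6.6); two-sided α = 0.05 (Protocol 11.4); entry PCT at or below 0.25 ng/mL (Protocol 5.3); values below 0.05 set to 0.025 (SAP 8.3.1); improvement rate 57.6% (SAP 6.6), hence about 0.424 × 280 = 119 clinical failures per arm.

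**Assumptions.** Shares r_P and r_A of placebo and azithromycin subjects have a rise above all other changes (risers); everyone else has the same distribution in both arms.

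**Step 1: what each quantity sees.**
- Mean difference ≈ (r_P − r_A) × average rise.
- P(X>Y) + 0.5 P(X=Y) = 0.5 + (r_P − r_A)/2, however high the rises are.

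For 6% against 2%, with risers reaching 0.5 to 2 ng/mL (average 1.25) from a baseline near 0.06, the mean difference is 0.04 × (1.25 − 0.06) ≈ 0.048 ng/mL. The rank probability is 0.52.

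**Step 2: approximate power of the rank test.** The SAP 8.2.8 variance without ties gives SE = √[(280 + 280 + 1)/(12 × 280 × 280)] = √(561/940,800) = 0.0244. So z = 0.02/0.0244 = 0.82, and power ≈ 1 − Φ(1.96 − 0.82) + Φ(−1.96 − 0.82) ≈ 13%.

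**Step 3: effect of ties.** If a share t of all changes is tied at exactly zero, the tie correction multiplies the variance by about 1 − t³.

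| t | 1 − t³ | z | Wilcoxon power |
|---|---|---|---|
| 0 | 1.000 | 0.82 | 13% |
| 0.5 | 0.875 | 0.88 | 14% |
| 0.7 | 0.657 | 1.01 | 17% |
| 0.9 | 0.271 | 1.57 | 35% |
| 0.96 (all non-risers) | 0.115 | 2.41 | 67% |

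Ties at zero therefore help the rank test to see risers. The size of the conflict depends on a share that the documents do not give.

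**Step 4: simulation.** All runs use 280 per arm unless stated, with an assumed log-normal baseline truncated at 0.25.

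| Scenario | Wilcoxon rejects | Bootstrap CI excludes 0 |
|---|---|---|
| Risers 6% vs 2%, baseline median 0.05 | 14% (12–19% for medians 0.03–0.08) | 64% |
| Risers 5% vs 1% | 13% | 84% |
| 5 placebo risers, 0 azithromycin, Day 5 PCT 0.5–5 | 7.5% | 99% |
| 119 per arm (failure rows), risers 8% vs 2% | 12% | 57% |
| Equal risers, log shift 0.15 in one arm | 99% | 14% |
| No difference, no risers | about 5% | about 5–6% |

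The first two rows agree with Steps 2 and 3. For 5 against 0, Step 1 gives 0.5 + 5/560 = 0.509, so z = 0.0089/0.0244 = 0.37 and power is about 7%. With 8 placebo risers and a slight fall in the other placebo subjects (log shift −0.3), both results were significant in opposite directions in 87% of trials.

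**Step 5: is the bootstrap interval a sound test?** Not quite. With identical arms containing rare risers (0.5–1%), it excluded 0 in about 7 to 10% of trials instead of 5%. In the 5 against 0 case, a placebo resample contains no riser with probability (1 − 5/280)^280 ≈ 0.6%, so the interval excludes 0 almost automatically, while Fisher's exact test of 5/280 against 0/280 gives p = 0.061. The 99% in the table partly reflects this.

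**The case against.** The strongest reply is that nothing is hidden and nothing turns on the p-value. Table 62 prints the CI for the mean difference with SD, median and range, by clinical outcome, and Listing 12 gives every subject's PCT. The analysis is exploratory and limited to ATP-5. SAP 8.1.1 rests non-inferiority on the primary analysis alone. A rank test is a reasonable choice for skewed PCT data, and no document says which kind of PCT change matters. All of this stands, and it makes the point minor. It does not make the description of the test correct.

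A reader might infer that the planned p-value would conceal bacterial infections missed in the placebo arm. The documents do not support that. The exploratory objective compares PCT levels among treatment failures, and the outcome measure is mean change overall and by clinical response; neither names a search for a minority of risers. ATP-5 also requires five doses by Visit 3, so subjects who stop study product early because they need other antimicrobials tend to leave it. Riser rates such as 6% have no basis in the plan.

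A reader might also infer that the bootstrap interval should replace the Wilcoxon test. Step 5 shows that this exchanges one problem for another.

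**Conclusion.** The mismatch holds as a matter of wording and needs no assumption: both documents call a rank-sum p-value the significance of a difference in means, and no other section corrects it. That the p-value and the CI can conflict in either direction follows from the different nulls. How often they would conflict cannot be known. With 6% against 2% risers, Wilcoxon power runs from 13% to 67% according to the share of zero changes, and all the simulated rates rest on assumed PCT distributions and riser rates. Severity is minor. The correction protects the reading of one exploratory table and has no bearing on the non-inferiority conclusion.

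**What to change.** In SAP 8.3.1 and Table 62 footnote c:

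1. Keep the Wilcoxon test, but describe it as a comparison of the distributions of PCT change.
2. Print its matching estimate, P(higher change on placebo) + 0.5 P(equal), with a CI from inverting the same test, using the tie-corrected formula already in SAP 8.2.8. A Hodges-Lehmann shift is less useful, since with many zero changes it may itself be near zero.
3. State that no conclusion about the mean difference is drawn from this p-value. If a p-value for the means is wanted, use a studentised permutation test. It is exact when the arms have identical distributions and only approximate when the means are equal but the shapes differ. A Welch test rejected in 14–21% of simulated trials with nearly equal means and rare risers, so caution is needed with any mean-based test here.
4. Add the CI and p-value inconsistency note already used in SAP 8.2.9 to 8.2.13.

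The cost is a sentence or two, one footnote and one extra row in Table 62. No new data are needed, and the protocol's Wilcoxon test is still reported, under a correct label.
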